6.1 Serious Adverse Events

An SAE is any untoward medical occurrence that at any dose:

- results in death
- is life-threatening (defined as an event in which the subject was at risk of death at the time of the event; it does not refer to an event which hypothetically might have caused death if it were more severe)
- requires inpatient hospitalization or causes prolongation of existing hospitalization (see NOTE below)
- results in persistent or significant disability/incapacity
- is a congenital anomaly/birth defect
- is an important medical event (defined as a medical event(s) that may not be immediately life threatening or result in death or hospitalization but, based upon

appropriate medical and scientific judgment, may jeopardize the subject or may require intervention [eg, medical, surgical] to prevent one of the other serious outcomes listed in the definition above.) Examples of such events include, but are not limited to, intensive treatment in an emergency room or at home for allergic bronchospasm; blood dyscrasias or convulsions that do not result in hospitalization.) Potential drug induced liver injury (DILI) is also considered an important medical event.

Suspected transmission of an infectious agent (eg, pathogenic or nonpathogenic) via the study drug is an SAE. Although pregnancy, overdose, cancer, and potential drug induced liver injury (DILI) are not always serious by regulatory definition, these events must be handled as SAEs.

NOTE:

The following hospitalizations are not considered SAEs in clinical studies:

- a visit to the emergency room or other hospital department < 24 hours, that does not result in admission (unless considered an important medical or life-threatening event)
- elective surgery, planned prior to signing consent
- admissions as per protocol for a planned medical/surgical procedure
- routine health assessment requiring admission for baseline/trending of health status (e.g., routine colonoscopy)
- medical/surgical admission other than to remedy ill health and planned prior to entry into the study. Appropriate documentation is required in these cases
- admission encountered for another life circumstance that carries no bearing on health status and requires no medical/surgical intervention (eg, lack of housing, economic inadequacy, caregiver respite, family circumstances, administrative reason).
- Admission for administration of anticancer therapy in the absence of any other SAEs (applies to oncology protocols)

6.1.1 SAE Collection and Reporting

Following the subject's written consent to participate in the study, all SAEs, whether related or not related to study drug, must be collected, including those thought to be associated with protocol-specified procedures. All SAEs must be collected that occur during the screening period and within 100 days of discontinuation of dosing.

The investigator should report any SAE that occurs after these time periods and that is believed to be related to study drug or protocol-specified procedure.

An SAE report should be completed for any event where doubt exists regarding its seriousness.

If the investigator believes that an SAE is not related to study drug but is potentially related to the conditions of the study (such as withdrawal of previous therapy or a complication of a study procedure), the relationship should be specified in the narrative section of the SAE Report Form.

REPORTING OF SAES

All events meeting the definition of a serious AE should be reported according to the departmental SAE checklist and SAE form. The initial SAE form should be sent to the following within 24 hours/1 business day of the Principal Investigator becoming aware:

1. Sponsor-Investigator
2. [contact]
3. Local Institutional Review Board when reporting requirements are met.

In addition to completing appropriate patient demographic and suspect medication information, the report should include as applicable the following information that is available at the time of report within the Sections B and C of the departmental SAE form:

- CTCAE term(s) and grade(s)
- current status of study drug
- all interventions to address the AE (testing and result, treatment and response)
- hospitalization and/or discharge dates
- event relationship to study drug

Follow-up reports:

Additional information may be added to a previously submitted report by adding to the original departmental SAE form and submitting it as follow-up or creating supplemental summary information and submitting it as follow-up with the original departmental SAE form.

6.2 Laboratory Test Result Abnormalities

The following laboratory test result abnormalities should be captured on the non-serious AE CRF page or SAE Report Form (paper or electronic) as appropriate:

- Any laboratory test result that is clinically significant or meets the definition of an SAE
- Any laboratory test result abnormality that required the subject to have study drug discontinued or interrupted
- Any laboratory test result abnormality that required the subject to receive specific corrective therapy. It is expected that wherever possible, the clinical rather than

laboratory term would be used by the reporting investigator (eg, anemia versus low hemoglobin value).

6.3 Pregnancy

If, following initiation of the study drug, it is subsequently discovered that a study subject is pregnant or may have been pregnant at the time of study exposure, including during at least 5 half-lives after product administration, the investigator must immediately notify the BMS Medical Monitor/designee of this event and complete and forward a Pregnancy Surveillance Form to BMS Designee within 24 hours and in accordance with SAE reporting procedures described in Section 6.1.1. In most cases, the study drug will be permanently discontinued in an appropriate manner (eg, dose tapering if necessary, for subject safety). In the rare event that the benefit of continuing study drug is thought to outweigh the risk, after consultation with BMS, the pregnant subject may continue study drug after a thorough discussion of benefits and risk with the subject Protocol-required procedures for study discontinuation and follow-up must be performed on the subject unless contraindicated by pregnancy (eg, x-ray studies). Other appropriate pregnancy follow-up procedures should be considered if indicated. The investigator must immediately notify the BMS (or designee) Medical Monitor of this event and complete and forward a Pregnancy Surveillance Form to BMS (or designee) within 24 hours and in accordance with SAE reporting procedures described in Section 6.1.1. Follow-up information regarding the course of the pregnancy, including perinatal and neonatal outcome and, where applicable, offspring information must be reported on the Pregnancy Surveillance Form.

Any pregnancy that occurs in a female partner of a male study participant should be reported to BMS. Information on this pregnancy will be collected on the Pregnancy Surveillance Form

6.4 Overdose

An overdose is defined as the accidental or intentional administration of any dose of a product that is considered both excessive and medically important. All occurrences of overdose must be reported as an SAE (see Section 6.1.1 for reporting details).

6.5 Other Safety Concerns

Any significant worsening noted during interim or final physical examinations, electrocardiogram, X-ray filming, any other potential safety assessment required or not required by protocol should also be recorded as a non-serious or serious AE, as appropriate, and reported accordingly.

7. DATA MONITORING COMMITTEE AND OTHER EXTERNAL COMMITTEES

Investigator/Sub-investigators, regulatory, CRS management, clinical research coordinators, clinical research associates, data managers, and clinic staff meet regularly in disease center Data Safety Monitoring Boards (DSMB) to review and discuss study data to include, but not limited to, the following:

- SAEs
- subject safety issues
- recruitment issues
- accrual
- protocol deviations
- unanticipated problems
- breaches of confidentiality

Minutes from the disease center DSMB meetings are available to those who are unable to attend in person.

All toxicities encountered during the study will be evaluated on an ongoing basis according to the NCI Common Toxicity Criteria Version 5.0. All study treatment associated AEs that are serious, at least possibly related and unexpected will be reported to the IRB. Any modifications necessary to ensure subject safety and decisions to continue or close the trial to accrual are also discussed during these meetings. If any literature becomes available which changes the risk/benefit ratio or suggests that conducting the trial is no longer ethical, the IRB will be notified in the form of an Unanticipated Problem submission and the study may be terminated.

All study data reviewed and discussed during these meetings will be kept confidential. Any breach in subject confidentiality will be reported to the IRB in the form of an Unanticipated Problem submission. The summaries of these meetings are forwarded to the UPMC Hillman Cancer Center DSMC which also meets monthly following a designated format.

For all research protocols, there will be a commitment to comply with the IRB's policies for reporting unanticipated problems involving risk to participants or others (including AEs). DSMC progress reports, to include a summary of all serious AEs and modifications, and approval will be submitted to the IRB at the time of renewal.

Protocols with participants in long-term (survival) follow-up or protocols in data analysis only, will be reviewed bi-annually.

Both the UPMC Hillman Cancer Center DSMC as well as the individual disease center

Phase I/II study of encorafenib and binimetinib with nivolumab and low dose ipilimumab in metastatic *BRAF* mutant melanoma

DSMB have the authority to suspend accrual or further investigate treatment on any trial based on information discussed at these meetings.

All records related to this research study will be stored in a locked environment. Only the researchers affiliated with the research study and their staff will have access to the research records.

8. STATISTICAL CONSIDERATIONS

This is a combination Phase I/II open label study of encorafenib +/- binimetinib + nivolumab + ipilimumab in participants with unresectable or metastatic BRAFV600-mutant melanoma. Two cohorts that differ by treatment (triple or quadruple therapy) will be enrolled in phase I. The recommended Phase II dosing regimen will be identified when following criteria are met:

- at least 10 patients have been evaluated on a regimen with DLT <60%
- the PI, Data and Safety Committee, [name] statistician, and interested PI's from participating institutions review all clinical data to determine the RP2R

Phase II will enroll two high risk cohorts differing by symptoms ((1) symptomatic brain metastases and 2) elevated liver enzymes with hepatic metastases) at the selected schedule and dose. The two cohorts will be investigated for safety and efficacy

8.1 Objectives

Primary Objective

- To nominate a recommended phase II regimen (RP2R) of triple or quadruple therapy with encorafenib +/- binimetinib + nivolumab and + ipilimumab in *BRAF* mutated, metastatic melanoma.

Secondary Objectives

- To estimate the RECIST response rate of triple or quadruple therapy in high risk populations of *BRAF* mutated, metastatic melanoma.
- To estimate the CNS clinical benefit rate (CBR, defined as complete response [CR] + partial response [PR] + stable disease [SD] >6 months) per RANO-MB criteria of triple or quadruple therapy in *BRAF* mutated, metastatic melanoma to the CNS
- To describe the toxicity, by CTCAEv5, of triple or quadruple therapy in *BRAF* mutated, metastatic melanoma
- To summarize the progression-free survival of triple or quadruple therapy in high risk populations of *BRAF* mutated, metastatic melanoma

Exploratory Objectives

6. To evaluate association between treatment response and baseline tumor mutational burden, changes in the tumor microenvironment (IFN associated gene expression), T cell clonality, and other biospecimens before and after triple or quadruple therapy.

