Phase II will take the RP2R schedule from Phase I and apply it to patients who may derive the most benefit from triple or quadruple therapy: Group 1) symptomatic brain metastases [up to 30 patients] and Group 2) LDH > 1x ULN with liver metastases OR bulky visceral disease (sum of longest diameter (SLD) > 44 mm) [up to 60 patients when combined with Group1].

Schema

Enrolled participants will be evaluated for safety and efficacy throughout the study and during follow up at the time points indicated on the time and events schedules presented in Tables 5.2.1 – 5.2.3. Response to treatment will be assessed in the intracranial (Group 1) and extracranial compartments (Group 2) and will be evaluated by serial radiographic assessment every 12 weeks until documented progression, withdrawal of consent, or the end of the study.

Follow-up Phase for each enrolled subject begins when the decision to discontinue a subject from study therapy is made (no further treatment with study therapy).

Participants will be followed for efficacy and OS. Treatment decisions will be based on local imaging evaluations using RANO-BM for intracranial lesions and RECIST 1.1 for extracranial lesions^{69,70}.

Additional imaging may be performed for patient care at the discretion of the investigator. All efficacy objectives will be based on Investigator assessment at the study site.

Safety will be evaluated for all treated participants using the NCI CTCAE version 5.0. Safety assessments will be based on medical review of AE reports, vital sign measurement results, physical examinations, and clinical laboratory tests.

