- c. Ten patients in each Phase Ib cohort will undergo fresh biopsy prior to treatment and between the 1st and 2nd doses of ipilimumab (between weeks 4-7). These will be the first 10 unless medical or societal factors (e.g. COVID19) limit the pursuit of research biopsies.
- d. During treatment: Every 12 weeks (± 7 days). End of Treatment (EOT): if a scan was not conducted within 30 days prior to end of study treatment. Efficacy follow-up: Every 12 weeks starting from the last assessment until documented disease progression per RECIST 1.1 (unless meeting criteria for treatment beyond progression), withdrawal of consent, lost to follow-up, or death irrespective of start of new anti-neoplastic therapy.

e. Table 5.2.2: Phase I Cohort 2																
Trial Period:		Screen Phase	Treatment										End of Treatment	Post-Treatment		
Treatment Cycle/Title:		Screen	D1 W1	D1 W2	D1 W3	D1 W4	D1 W5	D1 W6	D1 W7	D1 W8	D1 W9	D1W 10	D1W 14 (+)	Discon	Safety Follow-up	Follow Up Visits
Scheduling Window (Days):	28 days	± 3	± 3	± 3	± 3	± 3	± 3	± 3	± 3	± 3	± 3	± 3	± 3	At time of Discon	100 days post discon	Every 12 weeks post discon
Informed Consent	X															
Inclusion/Exclusion Criteria	X															
Demographics and Medical History	X															
Prior and Concomitant Medication Review	X	X			X			X			X	X				
Trial Treatment Administration ^a		X			X			X			X	X				
Review Adverse Events	X	X			X			X			X	X				
Nursing Call Check-Up			X	X		X	X		X	X		X				
Physical Examination	X	X			X			X			X	X		X		X
Vital Signs	X	X			X			X			X	X		X		X
ECOG Performance Status	X	X			X			X			X	X		X		X
Pregnancy Test	X															
EKG	X															
CBC with Differential	X	X	X	X	X			X			X	X		X		X
Comprehensive Serum Chemistry Panel	X	X	X	X	X			X			X	X		X		X
HCV, HIV, HepB	X															
TSH (T3, FT4 if TSH abnormal)	X	X	X	X	X			X			X	X		X		X
Research blood collection ^b	X				X									X		
Archival tumor collection	X															
Fresh tumor biopsy ^c	X				X ^c											
Imaging ^d	X															

- a. Encorafenib and binimeteinib are given continuously. Nivolumab and ipilimumab are given for four doses every 3 weeks then nivolumab is given monthly for up to one year.
- b. Blood will be drawn at baseline, week 4, week 12 (or with first restaging imaging) and at progression/end of treatment

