5.3 Efficacy Assessments

Assessment of extracranial disease (by CT scan or other approved modalities) and intracranial disease (by MRI scan) will be performed per the schedule above and using criteria in Appendix 5. Investigators may obtain more frequent follow-up MRI scans as medically indicated. Baseline assessments should be performed within 28 days prior to first dose of study drug utilizing CT or MRI for systemic lesions and within 28 days for brain lesions (MRI only). In addition to chest, abdomen, pelvis, and brain, all known sites of disease should be assessed at baseline. Subsequent assessments should include chest, abdomen, pelvis, brain, and all known sites of disease and should use the same imaging method as was used at baseline. Participants will be evaluated for tumor response beginning at 12 weeks (\pm 7 days) and every 12 weeks (\pm 7 days) thereafter, until disease progression is documented, or treatment is discontinued (whichever occurs later).

For extracranial disease assessment, contrast-enhanced computed tomography (CT) scans acquired on dedicated CT equipment is preferred for this study. CT with contrast of the chest, abdomen and pelvis and other areas of disease are to be performed for tumor assessments as above. Should a subject have a contraindication for CT IV contrast, a non-contrast CT of the chest and a contrast enhanced MRI of the abdomen and pelvis may be obtained. MRI's should be acquired with slice thickness of <5 mm with no gap (contiguous). Use of CT component of a PET/CT scanner: Combined modality scanning such as with FDGPET/CT is increasingly used in clinical care and is a modality/technology that is in rapid evolution; therefore, the recommendations outlined here may change rather quickly with time. At present, low dose or attenuation correction CT portions of a combined FDG-PET/CT are of limited use in anatomically based efficacy assessments and it is therefore suggested that they should not be substituted for dedicated diagnostic contrast enhanced CT scans for anatomically based RECIST measurements. However, if a site can document that the CT performed as part of a FDGPET/CT is of identical diagnostic quality to a diagnostic CT (with IV and oral contrast) then the CT portion of the FDG-PET/CT can be used for RECIST 1.1 measurements. Note, however, that the FDG-PET portion of the CT introduces additional data which may bias an investigator if it is not routinely or serially performed.

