8.2 Endpoints

The primary endpoint is the frequency of DLTs that are classified as either possibly, probably, or definitely related to study treatment according to NCI Common Terminology Criteria for Adverse Events (CTCAE v5.0). DLTs are specified in section 4.5.2. Adverse events and DLTs will be compiled separately for each phase I cohort (triple and quadruple therapy). Any patient receiving at least one dose any of study drug will be evaluable for toxicity.

Secondary endpoints include the clinical response rates in the phase II cohorts by RECIST criteria with a lower one sided 80% confidence interval. The clinical benefit rate (rate of complete response, partial response or stable disease) will also be computed with a lower one-sided confidence bound for the symptomatic brain metastasis group. Both clinical response and clinical benefit rates will apply to evaluable patients defined as having completed 4 weeks of therapy.

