8.4 Proposed Analysis of Primary and Secondary Endpoints

Based on NCI Common Terminology Criteria for Adverse Events (CTCAE v5.0), the term toxicity is defined as AEs that are classified as either possibly, probably, or definitely related to study treatment. The maximum grade for each type of toxicity will be recorded for each patient, and frequency tables will be reviewed to determine toxicity patterns. The number of occurrences of each event will be tabulated by event and grade. In addition, the total number of patients experiencing AEs over their course of treatment will be characterized by type of AE and grade. For this summary grades will be grouped into Grade I/II vs III/IV. In addition, the number of patients experiencing a dose-limiting toxicity as defined in table 4.5.2 will be compiled. Inferences regarding recommended phase II regimen and safety in both phase I and phase II cohorts will be made by calculating the proportion of patients with a dose-limiting toxicity with a one sided upper 90% confidence bound.

For the phase II cohorts, both the objective response rate (complete or partial response) / total evaluable) and the clinical benefit rate (complete or partial response + stable disease / total evaluable) will be computed with lower 80% confidence bounds. Evaluable patients are those who got at least one dose of ipi/nivo. Progression-free survival will be estimated with 90% two-sided confidence intervals for each phase II cohort. For progression-free survival, an event is defined as disease-progression or death.

For exploratory biomarker analyses, Spearman's correlation will be used for continuous variables such as Ki67+, T cell-inflamed GEP, pathway enrichment scores, TMB and others. Wilcoxon rank-sum test will be used to compare TMB between groups. Fisher's exact test will be used to compare the fraction of mutated and non-mutated samples per gene and R vs NR between T cell-inflamed and non-inflamed groups. Recognizing RNAseq values are relative, we created a frozen reference set from TCGA using our previous work and bring newly collected samples to the same baseline by comparing to this reference. We transform new data into the reference set using linear regression and determining per sample T cell-inflamed score (>8.24; T cell-inflamed, <6.43; non-T cell-inflamed and others intermediate). Benjamini-Hochberg procedure will be used to control FDR from multiple comparisons. All tests will be two-sided.

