When nodal disease is included in the sum of target lesions and the nodes decrease to “normal” size (< 10 mm), they may still have a measurement reported on scans. This measurement should be recorded even though the nodes are normal in order not to overstate progression should it be based on increase in size of the nodes. As noted earlier, this means that patients with CR may not have a total sum of “zero” on the case report form (CRF). Patients with a global deterioration of health status requiring discontinuation of treatment without objective evidence of disease progression at that time should be reported as “symptomatic deterioration.” Every effort should be made to document objective progression even after discontinuation of treatment. Symptomatic deterioration is not a descriptor of an objective response: it is a reason for stopping study therapy.

For equivocal findings of progression (eg, very small and uncertain new lesions; cystic changes or necrosis in existing lesions), treatment may continue until the next scheduled assessment. If at the next scheduled assessment, progression is confirmed, the date of progression should be the earlier date when progression was suspected.

5.10a DURATION OF RESPONSE

Duration of overall response: The duration of overall response is measured from the time measurement criteria are first met for CR/PR (whichever is first recorded) until the first date that recurrent or progressive disease is objectively documented (taking as reference for progressive disease the smallest measurements recorded on study). The duration of overall complete response is measured from the time measurement criteria are first met

for CR until the first date that recurrent disease is objectively documented. Duration of stable disease: Stable disease is measured from the start of the treatment (in randomized trials, from date of randomization) until the criteria for progression are met, taking as reference the smallest sum on study (if the baseline sum is the smallest, this is the reference for calculation of PD).

5.11a LESIONS THAT DISAPPEAR AND REAPPEAR

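### CNS clinical benefit: the objectives require stable disease beyond six months, Sections 8.2 and 8.4 do not, and no scheduled MRI falls at or just after six months

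*Combined protocol and SAP*

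**What the plan says.** **Definition in the objectives.** The Synopsis, Section 1.3 and Section 8.1 all define the CNS clinical benefit rate (CBR) as "complete response [CR] + partial response [PR] + stable disease [SD] >6 months".

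**Definition in the analysis text.** Section 8.2 has no minimum duration: "The clinical benefit rate (rate of complete response, partial response or stable disease) will also be computed". Nor does Section 8.4: "the clinical benefit rate (complete or partial response + stable disease / total evaluable").

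**Imaging schedule.** Section 3.1 says that response "will be evaluated by serial radiographic assessment every 12 weeks until documented progression". Section 5.3 says "Participants will be evaluated for tumor response beginning at 12 weeks", with a window of 7 days either side and the same interval afterwards. The Phase I schedule footnotes in Section 5.1 agree: "During treatment: Every 12 weeks (± 7 days"). Section 5.3 also allows extra scans: "Investigators may obtain more frequent follow-up MRI scans as medically indicated". The Synopsis instead gives an interval of 4 to 12 weeks for recording efficacy.

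**SD clock.** Appendix 5, Section 5.10a: "Stable disease is measured from the start of the treatment", and it ends when the progression criteria are met. Section 5.3.1 dates a confirmed progression to the scan that first showed it.

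No section says whether SD at the week-24 scan meets the six-month condition, or how to classify a patient with SD at week 24 and no later scan.

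**The concern.** CBR in the brain-metastasis group is a named secondary objective. It is reported from about 30 patients, in an open-label trial that uses investigator assessment. The plan gives two definitions of it, and the stricter one sets a threshold that falls between two scheduled scans. Patients with the same week-24 finding can then be classified differently because of when, or whether, the next MRI is done. Group 1 has symptomatic brain metastases, so symptom-driven extra MRIs and missing later scans are both foreseeable. If the rule is left open, the definition and the handling of these patients would be chosen after the data are known.

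**Working it through.** The plan states no figure for this timing, so there is none to reproduce.

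**1. Scan days against the threshold.** Inputs: 12-week interval with a 7-day window (Sections 5.1 and 5.3) and SD counted from treatment start (5.10a). Scan day = 7 × week ± 7. One calendar month = 365.25/12 = 30.44 days, so six months = 182.6 days.

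- Week 24: 168 ± 7 = days 161-175, or 5.29-5.75 months. This is 182.6 − 175 = 7.6 to 182.6 − 161 = 21.6 days before six months.
- Week 36: 252 ± 7 = days 245-259, or 8.05-8.51 months. This is 62.4 to 76.4 days after six months.
- If windows accumulate from scan to scan, the second scan can be as late as 168 + 14 = day 182 (5.98 months), still short.
- The documents do not define a month. With 28-day months, week 24 is exactly 6.0 and its window runs from 5.75 to 6.25, so it straddles the threshold.

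**2. Three patients with SD at week 24, classified under 8.1 with 5.10a.**

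| After week 24 | SD duration | Clinical benefit? |
|---|---|---|
| Progression first seen at the week-36 MRI | 252 d = 8.3 months | Yes |
| Progression seen on an extra MRI at week 25 | 175 d = 5.7 months | No |
| No later scan | Not determined | No rule given |

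Under the formula in 8.2 or 8.4, all three count as benefit.

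**3. Size of the gap.** An extra MRI can change the classification only if it shows progression after the week-24 scan and before day 183. Assume exponential time to intracranial progression, S(t) = 2^(−t/median), with the scan on day 168 (5.52 months). The plan gives no median for this regimen, so a range is shown.

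| Median (months) | S(24 weeks) | S(6 months) | Difference | × 30 patients | Difference / S(24 weeks) |
|---|---|---|---|---|---|
| 4 | 0.384 | 0.354 | 0.031 | 0.9 | 8.0% |
| 6 | 0.529 | 0.500 | 0.029 | 0.9 | 5.4% |
| 9 | 0.654 | 0.630 | 0.024 | 0.7 | 3.6% |
| 12 | 0.727 | 0.707 | 0.020 | 0.6 | 2.7% |

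With the scan at the early edge of its window (day 161) and a 4-month median, S = 0.400. Then (0.400 − 0.354) × 30 is about 1.4 patients. All these figures treat every non-progressor as SD and assume that an MRI falls in the gap, so they are upper limits for the effect of extra scans.

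**4. What one patient is worth.** In Table 8.4 the 80% lower bound for 10 of 30 is 25% and for 11 of 30 is 28%. Reclassifying one patient moves the bound by about 3 points.

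**The case against.** The best defence is that this is ordinary interval censoring in a single-arm secondary estimate. The week-24 scan is only 8-22 days short of six calendar months. Section 5.1 also calls the every-4-week nivolumab phase monthly, and on that usage week 24 is six months. No decision rule is attached to CBR, and Section 8.3 describes the 80% bound as suggestive only. All of this stands. It limits the size of the problem but does not supply the missing rule.

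Three stronger readings are tempting, and the documents do not support them.

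- A reader might infer that every week-24 SD patient who progresses by week 36 has a status that depends on scan timing. On the same exponential model that would be 38%, 27%, 19% and 15% for medians of 4, 6, 9 and 12 months, or 3-4 of 30 patients. But progression between about day 183 and week 36 means SD beyond six months whether an extra MRI or the scheduled one finds it. Only the short gap in the working is exposed.
- A reader might infer that the problem exists under either CBR formula. It does not: 8.2 and 8.4 have no duration, so nothing in them can be mistimed.
- A reader might infer that SD at week 24 with no later scan is a stated failure. It is undefined. Such losses are also limited, because Section 5.3 continues imaging until progression or treatment discontinuation, whichever is later, and the Phase I schedule footnotes provide for end-of-treatment and post-discontinuation scans.

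**Conclusion.** The concern holds in a limited form. The objectives conflict with Sections 8.2 and 8.4 on whether SD needs a minimum duration. If the objectives govern, no scheduled MRI falls at or just after six calendar months, and the plan does not tie the threshold to a scan. Only the SD component is affected, since complete and partial responses carry no six-month condition.

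For extra MRIs the effect is small: about 3-8% of week-24 non-progressors, 2-3 percentage points, under 1 of 30 patients. This rests on exponential progression with a median of 4-12 months, a scan on day 168 and calendar months. Patients with no later scan add to this by a number that cannot be estimated from the documents. The correction is still worth making before Group 1 patients are classified, because it is cheap and decides who counts as having benefit.

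**What to change.** Use one CBR definition in the Synopsis and Sections 1.3, 8.1, 8.2 and 8.4:

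- Clinical benefit is CR or PR, subject to the confirmation rule in 5.3.1, or SD with no progression through the week-24 MRI (day 161 or later).
- A patient who misses the week-24 MRI but has a later non-progressing MRI counts as benefit.
- A patient with no MRI at or after day 161 and no CR or PR counts as no benefit.
- Scans after the week-24 MRI do not reverse the classification. A confirmatory scan under 5.3.1 that settles an equivocal week-24 reading is part of that reading, because 5.3.1 dates confirmed progression to the initial scan.

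In the same amendment, reconcile the 4-to-12-week interval in the Synopsis with the 12-week schedule. Also reconcile the two definitions of evaluable: 8.2 requires four weeks of therapy, and 8.4 requires at least one dose of ipilimumab/nivolumab. The CBR denominator depends on which applies.

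The cost is wording only, with no added scans. The downside is that the threshold becomes 24 weeks (about 5.5 months) instead of six calendar months. If a true six-month threshold is wanted, the alternative is a scheduled MRI after day 183, which adds a scan.
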